1.3. STUDY DESIGN

This study is a two-arm randomised controlled trial testing a short course of tCBT against usual care. Subjects will be eligible if they are evaluated as “at high risk” of developing CWP, namely have had a primary care consultation with regional pain and at least two of: a maladaptive behavioural response to illness, a high number of somatic symptoms and/or sleep disturbance. If successful this study would provide general practitioners with an intervention option to reduce the risk of CWP development.

1.4. SAMPLE SIZE CALCULATIONS

Our previous longitudinal study of onset of CWP (and subsequent replication) has suggested that 21% of "high risk" persons identified will develop CWP over the course of the next twelve months. Our previous data is based on persons with pain and at least 2 out of 3 other "risk factors". There are no published studies of prevention of CWP on which to base our measure of effect. However in the MUSICIAN study some subjects, although reporting CWP at the screening survey, no longer had CWP at the enrolment interview. They were however still eligible to take part, provided they had regional pain. Therefore those subjects with regional pain provide a sub-population on which to base the likely effects of the tCBT. Amongst such subjects, those who received tCBT had a reduced odds of having CWP at the end of the study OR 0.5 95% CI (0.2-1.4) compared to those in usual care.

Thus the study is powered on the ability of the current study to reduce the onset of CWP from 21% to 12%, with 90% power and a 5% significance level. We further assume, based on prior data, that 75% of persons allocated to the tCBT arm will be adherent to the intervention, and that 80% of all subjects will return the follow-up questionnaires to assess outcome.

Final Sample Size

Accordingly we require 473 subjects per arm that is a total of 946 subjects recruited. In MUSICIAN exactly 50% of those found eligible and willing to consider taking part ultimately were randomised. A previous trial of a cognitive-behavioural intervention to prevent chronic pain found that 36% of patients identified as eligible ended up being recruited to the study. If 80% of eligible patients agreed to be contacted about taking part, this equates to 45% of those eligible and willing to consider taking part being randomised - higher numbers for a clinical trial of CWP reflect the fact that this is a prevention trial rather than a treatment trial and may be less attractive to potential participants. Thus we aim to find a total of 2102 subjects who are eligible and willing to consider taking part. Assuming a participation rate to the survey of 30%, that 1 in 4 people will be "at risk", and (using data from MUSICIAN) that 80% of people who return a questionnaire agree to consider taking part, we require to survey 35,037 persons.

1.5. STUDY POPULATION

Three health boards in Scotland will be research sites for the study. The three health boards are NHS Grampian, NHS Highland, and NHS Greater Glasgow and Clyde. We will require the involvement of 7 or 8 equivalent general practices. We will mail a randomly selected sample of adults aged 25 years and over registered with participating general practices in the study areas.

Searches are undertaken at each GP practice before the screening survey questionnaires are sent out by Health Informatics Centre Services in Dundee on behalf of the practice. Patients will return completed survey questionnaires to the research team at the University of Aberdeen where they will be assessed by the research team for eligibility and sent invitation letters if eligible.

The “screening questionnaire” will determine whether a) they meet the study eligibility criteria and b) they would be willing to be contacted again regarding a treatment trial for “musculoskeletal health”. Specific criteria for inclusion and exclusion of participants can be found in the protocol (version 4.0 26/02/2016).

A list of eligible patients will be provided to the general practitioner in advance, with the option of indicating any as unsuitable for the study. Patients would then be sent information about the study and subsequently contacted by a member of the research team by telephone and, if appropriate, consented and recruited into the trial.

1.6. STATISTICAL ANALYSIS PLAN (SAP)

1.6.1.SAP OBJECTIVE

The objective of this SAP is to describe the quantitative statistical analyses to be carried out for MAMMOTH. This SAP is based on protocol version 4 (26/02/2016). Future amendments to the protocol will be reviewed for their impact on this SAP, which will be updated only if necessary and any changes to the SAP will be documented under version control.

1.6.2.GENERAL PRINCIPLES

Categorical variables will be described with number and % in each category. Continuous variables will be described with mean and standard deviation (SD) or median and inter-quartile range (IQR) depending on their distribution. The amount of missing data will be provided for each variable.

ABBREVIATIONS

CI	Confidence Interval
CONSORT	Consolidated Standards of Reporting Trials
CRF	Case report form
CTA	Clinical Trial Authorisation
EQ-5D	European Quality of Life Questionnaire
ITT	Intention To Treat
PP	Per Protocol
RCT	Randomised Controlled Trial
SAP	Statistical Analysis Plan
SD	Standard Deviation
TSC	Trial Steering Committee

1.6.3.SOFTWARE

All analyses will be carried out using STATA version 14 (StataCorp. 2015. *Stata Statistical Software: Release 14*. College Station, TX: StataCorp LP). Data will be stored on a secure drive, with limited access to those who need it.

2. ANALYSIS

2.1. STUDY POPULATIONS

Comparison between arms will be on an intention-to-treat basis (main analysis) with a per protocol sensitivity analysis.

Intention to treat (ITT) population

Intention to treat analysis will be of all participants who were randomised and for whom at least one follow-up observation of the primary outcome is available. Participants will be analysed in the group to which they were randomised.

[figure not shown]
Per protocol (PP) population

Pre protocol analysis will be of all participants of the ITT population excluding participants who were not compliant with their randomised study arm. Non-compliance is defined as those not having any primary outcome data and/or those not completing treatment as in the definition below.

Full intervention will consist of an initial assessment (45-60 minutes), 6 weekly sessions (each 30-45 minutes) over six weeks, and then booster sessions at 3 and 6 months. The per protocol analysis will be those receiving the completed treatment (defined below) vs. all others.

A participant in the CBT group has completed treatment if: there is mutual agreement between therapist and participant to stop treatment AND at least one session (the initial assessment) has been attended; OR, participant has at least 3 sessions of CBT (including the initial assessment)

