### *Statistical analysis*

A pre-defined statistical analysis plan will be developed and signed off by the trial steering committee before undertaking any data analysis. Comparison between arms will be on an intention-to-treat basis (main analysis) with a per protocol sensitivity analysis.

Characteristics of the study participants in the two treatment arms will be described using simple summary statistics. Descriptive statistics will include mean and standard deviation for normally distributed continuous data, median and inter-quartile range for skewed continuous data and count and percentage for categorical data. No formal statistical comparisons will be made between baseline characteristics. Primary and secondary outcomes will be described at the three follow-up times: 3, 12 and 24 months, using appropriate summary statistics. The primary outcome is the between arm difference in the proportions of people developing CWP from baseline to follow-up. This comparison will be made using simple chi-squared tests at each follow-up time. Appropriate adjustment will be made for the stratification factor used in the randomisation (the number of non-pain "high-risk" factors that a participant reports at baseline) using multiple logistic regression.

Comparisons with appropriate hypothesis tests will be used for the secondary outcomes, pain, illness behaviour, somatic symptom reporting, sleep problems, quality of life and wellbeing, psychological distress, patient global impression of change measure and fatigue. Appropriate adjustment will be made for the stratification factor. Given the multiple secondary outcomes, the p-value used to denote statistical significance will reflect the multiple comparisons.

Mixed models analyses with an appropriate error structure will take into account the repeated assessment of the outcome data for the same patient across the three follow-up times. As part of sensitivity analyses, multiple imputation methods will be used, where appropriate, to address issues of missing data. However, these methods will not be applied if the use of imputation is contrary to specified rules for the relevant validated measurement scale.

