$\text{Logit}(p(\text{CWP})) = \text{constant} + \text{treatment effect} + \text{blocking effect} + \text{other covariate effects} + \text{random error}.$

The treatment effect will be a fixed effect. The blocking effect will comprise the number of high-risk factors present (fixed effect) and GP practice (random effect, n=16 practices).

The other covariates that will be considered in the model are: age and sex. The expectation is that these covariates will be balanced through randomisation, but they are both known to be related to the likelihood of the development of CWP. Multiple imputation (MI) analysis will be used to examine sensitivity to missing data.

After discussion at the TSC it was decided that it will not be possible to consider the therapist effect in a formal way between the two arms. Only one arm will be exposed to the therapists and even descriptive approach was disregarded as the number of participants was expected to vary widely between different therapists.

2.4.5.ANALYSIS OF SECONDARY OUTCOMES

Secondary outcomes

Comparisons with appropriate hypothesis tests will be used for the secondary outcomes, pain, illness behaviour, somatic symptom reporting, sleep problems, quality of life and wellbeing, psychological distress, patient global impression of change measure and fatigue. Appropriate adjustment will be made for the stratification factor. The baseline value of the relevant outcome variable will also be included as a covariate. Given the multiple secondary outcomes, the p-value used to denote statistical significance will reflect the multiple comparisons.

An appropriate adjustment will be made for the stratification factor as described above, the blocking effect will be addressed through including the number of high-risk factors present (fixed effect) and GP practice (random effect).

There are 8 secondary outcomes. The most conservative approach would be to use Bonferroni $p=0.05/8=0.00625$ or a family-wise error rate of $\alpha=0.0065$ (so $1-(1-\alpha)^8 = 0.05$). A less conservative approach would be to take $p=0.01$ for significance of the secondary outcomes and this was agreed as appropriate at the TSC meeting of 9 September 2016.

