2.4.7. MULTIPLE IMPUTATION METHODS

As part of sensitivity analyses, multiple imputation methods will be used, where appropriate, to address issues of missing data. However, these methods will not be applied if the use of imputation is contrary to specified rules for the relevant validated measurement scale.

Imputations of 100 repeat samples from the dataset will be used if processing speed allows. If not then at least 10-20 repeat samples will be used. MI routines within Stata will be employed using the relevant outcome variable and all risk factors that are candidates for inclusion in the relevant regression model (bearing in mind the restriction above).

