2.5. WITHDRAWALS

Participants will have the option to withdraw from the treatment or the study at any time. Those withdrawing from the treatment will continue to be sent follow-up questionnaires unless they specifically request not to receive them. Failure of any participant to complete a follow-up questionnaire at any particular time-point will not be counted as a withdrawal unless the participant requests not to receive any further follow-ups.

The number of participants withdrawing from the trial will be recorded within each randomised group. Details of reasons for withdrawal will be provided with the CONSORT diagram.

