Table 8: Primary outcome 12 month unadjusted and adjusted analysis of presence of CWP in the tCBT and usual care arms on the ITT population

	Unadjusted OR	95% CI	p-value	Adjusted OR	95% CI	p-value
Treatment: tCBT vs Usual care						
Number of high-risk factors present: 3 vs 2						
Age						
Gender						
Random effect: GP practice						

Table 9: Primary outcome 12 month unadjusted and adjusted analysis of presence of CWP in the tCBT and usual care arms on the PP population (sensitivity analysis)

	Unadjusted OR	95% CI	p-value	Adjusted OR	95% CI	p-value
Treatment: tCBT vs Usual care						
Number of high-risk factors present: 3 vs 2						
Age						
Gender						
Random effect: GP practice						

Table 10: Primary outcome 12 month unadjusted and adjusted analysis of presence of CWP in the tCBT and usual care arms on the ITT population with multiple imputation (sensitivity analysis)

	Unadjusted OR	95% CI	p-value	Adjusted OR	95% CI	p-value
Treatment: tCBT vs Usual care						
Number of high-risk factors present: 3 vs 2						
Age						
Gender						
Random effect: GP practice						

Table 11: Primary outcome 3 and 24 month adjusted analysis of presence of CWP in the tCBT and usual care arms on the ITT population

	3 months			24 months		
	Adjusted OR	95% CI	p-value	Adjusted OR	95% CI	p-value
Treatment: tCBT vs Usual care						
Number of high-risk factors present: 3 vs 2						
Age						
Gender						
Random effect: GP practice						

Table 12: Primary outcome 3 and 24 month adjusted analysis of presence of CWP in the tCBT and usual care arms on the PP population

	3 months			24 months		
	Adjusted OR	95% CI	p-value	Adjusted OR	95% CI	p-value
Treatment: tCBT vs Usual care						
Number of high-risk factors present: 3 vs 2						
Age						
Gender						
Random effect: GP practice						

Note: This table will be repeated for 3 months and 24 months

Table 13: Secondary outcome adjusted analysis of presence of pain in the tCBT and usual care arms on the ITT population

	3 Months			12 Months			24 Months		
	Adjusted OR	95% CI	p-value	Adjusted OR	95% CI	p-value	Adjusted OR	95% CI	p-value
Treatment: tCBT vs Usual care									
Number of high-risk factors present: 3 vs 2									
Age									
Gender									
Random effect: GP practice									

Note: As all patients have pain at baseline there is no adjustment for this as there is for other secondary outcomes

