Number of high-risk factors present: 3 vs 2			
Age			
Gender			
Random effect: GP practice			

Table 25-Table 30 similar for somatic symptoms, sleep problems, distress - General Health Questionnaire score, QoL from EQ5D score, QoL from ICECAP score, fatigue

Table 31: Secondary outcome adjusted analysis of Global impression of change measure score at 3, 12 and 24 months in multilevel model in the tCBT and usual care arms on the ITT population

	Multilevel at 3 time points		
	Adjusted coefficient	95% CI	p-value
Treatment: tCBT vs Usual care			
3 to 12 months			
12 to 24 months			
Number of high-risk factors present: 3 vs 2			
Age			
Gender			
Random effect: GP practice			

Note: Global impression of change measure score may not need to be adjusted for baseline.

Table 32: Responder analysis (tCBT treatment group)

	CWP at 12 months (n=)	No CWP at 12 months (n=)	p-value
Presence of pain n (%)			
Illness behaviour Score Median (IQR)			
Somatic symptom reporting			
Sleep problems Score Median (IQR)			
Gender n (%) Male Female			
Age n Mean (SD) Median (IQR)			
Health board n (%)			
Distress - General Health Questionnaire Median (IQR)			
QoL from EQ5D Median (IQR)			
QoL from ICECAP Median (IQR)			
Fatigue Median (IQR)			
Global impression of change measure Median (IQR)			
Completion of treatment n (%)			
Length of time between randomisation and treatment start Median (IQR)			

Table 33: Patient withdrawals

Reasons for withdrawal	tCBT (n=)	Usual Care (n=)	Total (n=)
Number who withdrew from the study (%)			
Primary reason for withdrawal ¹			

¹ Denominator is the number of patients that withdrew from the study.

Table 34: Distribution of withdrawals by baseline characteristics

	Withdrawals (n=)	Non-withdrawals (n=)
Gender n (%) Male Female	xx xx	xx xx
Age (n) Mean (SD) Median (IQR) (min, max)		
Presence of pain n (%)		
Illness behaviour Score > 4 n (%) Symptoms scale Score > 2 n (%) Sleep problems Score > 4 n (%)		
2 factors present n (%) 3 factors present n (%)		
GP practice n (%) Distress - General Health Questionnaire Median (IQR) QoL from EQ5D Median (IQR) QoL from ICECAP Median (IQR) Fatigue Median (IQR) Global impression of change measure Median (IQR)

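### The SAP's ITT set requires a follow-up CWP response, so the missing-data check and the baseline table leave out participants who never respond

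*SAP*

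**What the plan says.** The protocol (section 10, Statistical analysis) states the principle without any condition on follow-up: "Comparison between arms will be on an intention-to-treat basis (main analysis) with a per protocol sensitivity analysis".

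SAP 2.1 keeps the label but narrows the set to "all participants who were randomised and for whom at least one follow-up observation of the primary outcome is available", analysed as allocated.

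On missing data, SAP 2.4.4 says: "Multiple imputation (MI) analysis will be used to examine sensitivity to missing data". SAP 2.4.7 lists the imputation variables as "the relevant outcome variable and all risk factors that are candidates for inclusion in the relevant regression model". Neither section names a wider population. The title of the corresponding dummy table, Table 10, places the analysis "on the ITT population with multiple imputation (sensitivity analysis". Table 6 (baseline characteristics) is also headed as being in the ITT population.

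On losses, SAP 2.5 says that not returning a questionnaire "will not be counted as a withdrawal unless the participant requests not to receive any further follow-ups". Table 33 gives withdrawals and their reasons by arm. The table headed "Table 34: Distribution of withdrawals by baseline characteristics" has two columns, withdrawals and non-withdrawals, is not split by arm and names no population. SAP 2.4.3 promises a CONSORT diagram covering flow, withdrawals and exclusions after randomisation.

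**The concern.** Entry to the set depends on something that happens after randomisation, namely returning at least one usable follow-up. Return could differ by arm, since one arm is offered up to nine telephone contacts (one assessment, six weekly sessions, two boosters) and the other has nothing added to usual care.

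A narrower set under a different name would be an ordinary choice. The difficulty lies in where this set is used. The imputation table exists to ask whether missing outcomes matter, yet it starts from a set from which people with no outcome at all have been removed. Table 6 is meant to show that randomisation produced comparable arms, but shows them only after that selection. By their titles, no efficacy table covers everyone randomised: the per-protocol set is a subset of ITT, and the repeated-measures tables (22 to 31) use ITT too.

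What is at stake is whether the trial can show that its 12-month result withstands loss to follow-up.

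**Working it through.** **Who is excluded.** SAP 2.1 can be read in two ways.

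- *Any of 3, 12 or 24 months.* Tables 11 and 22 support this reading, because they call CWP at those times the primary outcome. Excluded: people with no response at any time. Someone with only a 3- or 24-month response is in the set but has no 12-month outcome, so the ITT n is neither the number randomised nor the number in Table 8. The per-protocol rule, which removes from ITT those lacking any primary outcome data, then removes nobody on that ground.
- *12 months only*, following the outcome definition in SAP 2.3.1. Excluded: everyone missing at 12 months. Table 10 would then have no missing outcome left to impute.

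Complete non-responders are outside Table 10 on either reading.

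**The plan's own figure.** Inputs from SAP 1.4 and 2.4.1: 21% v 12%, 90% power, two-sided 5%, 80% return.

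- Uncorrected: n = [1.96√(2 × 0.165 × 0.835) + 1.2816√(0.21 × 0.79 + 0.12 × 0.88)]² / 0.09² = 355.4, rounded up to 356 per arm.
- With continuity correction: (355.4/4) × [1 + √(1 + 4/(355.4 × 0.09))]² = 377.3, rounded up to 378.
- Allowing for return: 378/0.80 = 472.5, rounded up to 473 per arm, 946 in total. This matches the plan, so 20% non-return is the plan's own allowance.

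**How many could be affected.** Missing at 12 months: 0.20 × 946 = 189, about 95 per arm. Never-responders are a subset of these. The documents do not give their share. Assuming 20% non-return at each of the three times:

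- different people each time: about 0
- independent across times: 0.2³ = 0.8%, about 8 people
- the same people each time: 189

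**What informative non-response could do.** Assumptions, not in the documents: a fraction f of each arm never responds; tCBT responders have 12% CWP; tCBT never-responders and the whole usual-care arm have 21%. The whole-arm tCBT risk is (1 − f) × 12 + f × 21.

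| f | People of 946 | tCBT risk, % | Difference, points | Odds ratio |
|---|---|---|---|---|
| 0 | 0 | 12.00 | 9.00 | 0.51 |
| 0.8% | 8 | 12.07 | 8.93 | 0.52 |
| 5% | 47 | 12.45 | 8.55 | 0.54 |
| 10% | 95 | 12.90 | 8.10 | 0.56 |
| 15% | 142 | 13.35 | 7.65 | 0.58 |
| 20% | 189 | 13.80 | 7.20 | 0.60 |

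An analysis confined to responders shows 9.00 points in every row. The 20% row also shows what the planned figures would become if everyone missing at 12 months in the tCBT arm were given the usual-care risk.

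**Would widening Table 10 be enough?** No. With only the outcome and the analysis-model covariates in the imputation model, and under missing-at-random, complete non-responders add almost no information. Including them matters when auxiliary variables are added or when a not-missing-at-random assumption is tried. The SAP plans neither.

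**The case against.** Much of the opposing case stands.

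- **The primary estimate does not move.** A person with no response cannot contribute an observed outcome to Table 8 under any definition. A reader might infer that the definition itself biases the main result. It does not: the shrinkage in the table above measures informative non-response.
- **Direction is unknown.** A reader might infer that the exclusion favours tCBT. That needs tCBT non-responders to have a higher CWP risk than tCBT responders, and nothing in the documents says so.
- **Extreme bounds prove little.** At 10% never-responders, giving CWP to all of those in the tCBT arm and to none in usual care yields 0.9 × 12 + 10 = 20.8% v 0.9 × 21 = 18.9%, a change of sign. That bound would threaten any trial with such loss and is not evidence of a fault in this one.
- **The group may be small.** Protocol 6.6 plans telephone reminders and a one-sheet form at 3 and 12 months. At 24 months non-returners are telephoned and asked about pain sites and duration.
- **Losses are not hidden.** The CONSORT diagram, Table 33, the missing-data counts promised in SAP 1.6.2, and Table 2 set against Table 3 will together show numbers. A reader might also infer that Table 34 counts silent non-responders as retained. Its column says only non-withdrawals, and since it names no population they may not be in it at all.
- **The set has a rationale.** People with at least one observation are those who contribute to the planned mixed models over three times.

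None of this answers the narrower point. Counts do not give a baseline profile by arm or the effect on the estimate, and a set suited to the mixed model does not suit a check on missing data. The dummy tables are described as examples that may change in format, but no SAP text assigns Table 10 or Table 6 to a wider set.

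**Conclusion.** The concern holds as a fault of labelling and of scope. What the SAP calls ITT is an available-case set. Because Tables 6 and 10 are tied to it, the plan neither shows the arms as randomised nor tests the 12-month result against the loss of people who never respond. Table 34 does not fill the gap, since it profiles formal withdrawals only and pools the arms.

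The reading of the text is secure; the numerical consequence is not. The number affected is about 0 to 189 of 946 at 20% non-return. The fall from 9 points to about 8.6-7.7 rests on two assumptions: that 5-15% never respond, and that tCBT never-responders have the usual-care risk. At the independent-non-return figure of 0.8% the effect is negligible (8.9 points). The documents do not show that the primary result will be biased, or in which direction. They show that the planned tables could not examine the question. The correction is worth making before analysis, but it does not put the design or the sample size in doubt.

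**What to change.** 1. Define ITT in SAP 2.1 as all randomised participants in their allocated arm, and use that set for Tables 1, 3, 6 and 10. Reconcile the per-protocol wording on missing primary outcome data with it.
2. Label Table 8 as ITT participants with observed 12-month CWP, and state n by arm.
3. Run the Table 10 imputation on everyone randomised. Add CWP at 3 and 24 months and the baseline scores already collected as auxiliary variables.
4. Add a not-missing-at-random version in which every tCBT participant missing 12-month CWP is given the usual-care risk. This should cover those with only a 3- or 24-month response as well as never-responders, since both lack the primary outcome.
5. Add to Table 34 a baseline profile, by arm, of 12-month CWP observed versus missing, and name the population the table covers.

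The cost is SAP wording, table headings and a little more analysis. The sample size stays at 946. No new data are needed, because eligibility was determined from the screening questionnaire and those data exist for everyone randomised.
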